5.1 Overall Study Design Description

This is a Phase III, prospective, multicenter, within-patient comparison of UE-DSE and CE-DSE that will be conducted at 10-15 sites in subjects with a suboptimal LV EBD on non-contrast 2D transthoracic echocardiography with harmonic imaging at rest and that are scheduled for coronary angiography. Suboptimal LV EBD is defined as published in guidelines, having ≥ 2 adjacent segments on any apical view that are suboptimal^{1,12} during the rest non-contrast ultrasound examination.

Imaging conditions will be representative of those used in routine clinical practice and will include LV EBD, and LV wall motion using harmonic imaging modality with commercially available equipment.

Subjects who are enrolled in the study will undergo a rest non-contrast echocardiogram (UEUS) with the standard apical 4-, 2-, and 3-chamber views obtained with harmonic imaging. A 2 mL dose of LUMASON will be administered as an intravenous bolus injection during rest contrast enhanced echocardiography (CEUS). A recording of 2D transthoracic harmonic echocardiography images will be performed for both UEUS and CEUS rest imaging. At least 30 minutes after the completion of the rest unenhanced echocardiography (UEUS) and contrast enhanced-echocardiography (CEUS) the dobutamine infusion will begin. Once peak stress is achieved (with or without the addition of atropine), subjects will undergo unenhanced dobutamine stress echocardiography (UE-DSE). This will be followed by the contrast-enhanced dobutamine stress echocardiography (CE-DSE) with the administration of 2 mL of LUMASON. A recording of 2D transthoracic images will be performed for both UE-DSE and CE-DSE imaging. The on-site Investigators will provide an overall diagnosis of CAD for each subject from the unenhanced (UEUS and UE-DSE) and contrast-enhanced (CEUS and CE-DSE) echocardiographic images.

The truth standard in this study will be coronary angiography. If coronary angiography is not performed or is indeterminate subjects will be followed for up to 6 months to collect cardiac events.

An off-site assessment of the echocardiographic images will be performed by 3 blinded readers unaffiliated with any of the investigational sites, blinded to the subject's clinical information. The efficacy analysis will be based on the blinded reader evaluations of LV EBD, wall motion abnormalities and diagnosis of CAD.

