10.6 Efficacy Analysis

The echocardiographic images will be assessed by 3 off-site blinded readers independent of the investigational sites; accordingly, the efficacy analysis will be performed separately for each off-site reader. An additional, fourth, blinded reader will assess the coronary angiography images and provide a diagnosis of CAD.

10.6.1 Primary Efficacy Endpoint – Sensitivity and Specificity for Detection and Exclusion of CAD

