10.6.1.2 Evaluation of CAD

The overall diagnostic echocardiographic conclusion will be classified by the off-site readers as Normal, Abnormal or Unevaluable for unenhanced (UEUS and UE-DSE) and LUMASON-enhanced (CEUS and CE-DSE) echocardiography respectively.

The diagnostic performance of echocardiography (UE-DSE and CE-DSE) will be derived based on the diagnosis from stress echocardiography and diagnosis from truth standard (see Table E).

Table E: Cross Tabulation of Diagnosis: Truth Standard vs. Stress Echocardiography

Truth Standard (TS)	Stress Echocardiography		
	Normal	Unevaluable*	Abnormal
Negative	TN	FP	FP
Positive	FN	FN	TP

TN = true negative; TP = true positive; FN = false negative; FP = false positive

*Unevaluable is defined as: inadequate visualization of segments comprising all coronary artery territories due to motion artifacts, lateral wall drop out, swirling or attenuation artifacts.

The null hypothesis is that there is no difference in sensitivity/specificity between CE-DSE and UE-DSE at peak stress; the alternative hypothesis is that CE-DSE is superior to UE-DSE in terms of higher sensitivity/specificity:

$$H_0: \text{Diag}_{\text{CE}} - \text{Diag}_{\text{UE}} = 0,$$

$$H_a: \text{Diag}_{\text{CE}} - \text{Diag}_{\text{UE}} > 0;$$

where Diag_{CE} and Diag_{UE} denote sensitivity/specificity for CE-DSE and UE-DSE at peak stress respectively.

The sensitivity and the specificity along with their 95% confidence intervals (CIs) will be calculated, and the difference in sensitivity/specificity will be tested using McNemar's Chi-square 2-sided test.

In addition, inter-reader agreement for the detection/exclusion of CAD for CE-DSE and UE-DSE will be evaluated by kappa statistic.

10.6.2 Co-Primary Efficacy Endpoint – Critical Shift of Subjects with Suboptimal Images to Adequate Images

The co-primary endpoint: The proportion of subjects with suboptimal images (≥ 2 adjacent segments with inadequate LV EBD in any of the 3 apical views) at UE-DSE converted to adequate images (reduction of suboptimal adjacent segments to obtain adequate images) at CE-DSE will be estimated along with the 95% CIs.

Additionally, the following supportive analyses will be performed:

- proportion of subjects with optimal images at UE-DSE to suboptimal (≥ 2 adjacent segments with inadequate LV EBD in any of the 3 apical views) at CE-DSE in terms of LV EBD visualization will be estimated along with the 95% CIs.

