10.6.4 Success Criteria

The study will be considered a success if:

- for the primary efficacy endpoint of sensitivity/specificity, CE-DSE is superior to UE-DSE for at least 2 out of the 3 blinded readers and for the same 2 readers a lower limit of 2-sided 95% CI for sensitivity/specificity is $\geq 50\%$ (a rate considered greater than chance);
- for co-primary efficacy endpoint of proportion of subjects with critical shift of suboptimal images at UE-DSE to adequate images at CE-DSE, for at least 2 out of the 3 blinded readers lower limit of 2-sided 95% CI is above 35%.

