10.7 Sample Size

Software nQuery Advisor 7.0 is used for sample size determination in this study.

As suggested by FDA during the type C meeting on 13Aug2014, and as also reinforced and documented in the official meeting minutes issued by FDA on 24Sep2014, this study needs to demonstrate 1) a significant improvement in diagnostic performance endpoints, i.e., sensitivity/specificity from unenhanced stress imaging (UE-DSE) to contrast-enhanced stress

imaging (CE-DSE) in term of detection and exclusion of CAD, and 2) lower the CI of CE-DSE sensitivity and specificity greater than 50% (a rate greater than chance).

For significant improvement in diagnostic performance endpoints, the null hypothesis is that there is no difference in sensitivity/specificity between CE-DSE and UE-DSE at peak stress; the alternative hypothesis is that CE-DSE is superior to UE-DSE in terms of higher sensitivity/specificity:

$$H_0: \text{Diag}_{\text{CE}} - \text{Diag}_{\text{UE}} = 0,$$

$$H_a: \text{Diag}_{\text{CE}} - \text{Diag}_{\text{UE}} > 0;$$

where Diag_{CE} and Diag_{UE} denote sensitivity/specificity for CE-DSE and UE-DSE at peak stress respectively.

With 2-sided significance level (alpha) of 5%, and the probability of a Type II error (β) of 0.20, assuming expected difference between CE-DSE and UE-DSE is 25%,¹ and the proportion of discordant pairs is 40%, 45 subjects will be needed for sensitivity/specificity respectively.

For lower CI of CE-DSE sensitivity/specificity greater than 50%, assuming sensitivity/specificity of CE-DSE = 65%, about 45 CAD positive subjects are needed to have 95% confidence that the lower limit of sensitivity >50%, and 45 CAD negative subjects are needed to have 95% confidence that lower limit of specificity >50%.

Assuming approximately 30% of subjects enrolled will be CAD positive,¹³ in order to obtain 45 CAD positive subjects, 150 subjects in total need to be enrolled. With a total of 150 subjects enrolled, this will also provide more than enough CAD negative subjects according to the above calculations. The prevalence of positive subjects will be tracked based on on-site CAD diagnosis from the truth standard and if less than 30% of subjects are CAD positive, additional subjects will need to be enrolled to obtain sufficient CAD positive subjects.

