For the co-primary endpoint of critical shift from suboptimal at UE-DSE images to adequate images at CE-DSE, sample size assumptions are based on the results from the previous pivotal phase III Bracco-sponsored study (██████████).²² This study had 44.8%-46.0% of the subjects converted from suboptimal at UEUS to adequate at LUMASON-enhanced echocardiography (CEUS) at rest. When the sample size is 150, a 2-sided 95% CI for a single proportion using the large sample normal approximation will extend 8% from the observed proportion for an expected proportion of 45% subjects with critical shift from suboptimal at UE-DSE images to adequate images at CE-DSE. This can be translated as lower limit of 95% CI >35% for the observed proportion of subjects with critical shift.

Considering approximately 15% of subjects enrolled are anticipated to dropout, approximately 175 subjects will need to be enrolled.

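### Section 10.7 states the critical-shift precision on all 150 evaluable subjects, while 10.6.2 most naturally counts only those each reader scores suboptimal at unenhanced stress

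*Combined protocol and SAP*

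**What the plan says.** UE-DSE and CE-DSE are the unenhanced and contrast-enhanced peak-stress examinations.

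- **Endpoint (10.6.2).** The definition begins "The co-primary endpoint: The proportion of subjects with suboptimal images" and goes on to conversion from suboptimal at UE-DSE to adequate at CE-DSE. A supportive analysis runs the other way, on the "proportion of subjects with optimal images at UE-DSE to suboptimal" at CE-DSE. No denominator is named in so many words.
- **By reader (10.6).** There are three blinded readers; "accordingly, the efficacy analysis will be performed separately for each off-site reader".
- **Success rule (10.6.4).** The co-primary is met if "for at least 2 out of the 3 blinded readers lower limit of 2-sided 95% CI is above 35"%.
- **Precision (10.7).** "When the sample size is 150, a 2-sided 95% CI for a single proportion using the large sample normal approximation will extend 8"% around an expected 45%, which the section reads as a lower limit above 35%. The 45% comes from a previous study at rest, in which "44.8%-46.0% of the subjects converted from suboptimal at UEUS to adequate at LUMASON-enhanced echocardiography (CEUS) at rest". The base of that rate is not stated.
- **Where 150 comes from (10.7).** It is the number expected to yield 45 CAD-positive subjects at 30% prevalence, raised to about 175 for 15% dropout. It can grow: "if less than 30% of subjects are CAD positive, additional subjects will need to be enrolled to obtain sufficient CAD positive subjects".
- **Entry (5.1, 5.4.1).** Subjects enter with "suboptimal LV EBD on non-contrast 2D transthoracic echocardiography with harmonic imaging at rest". Nothing is required of the stress images.
- **Efficacy set (10.2).** The only one defined requires peak-stress data from both examinations and a definitive CAD diagnosis from the truth standard. It does not require suboptimal images at UE-DSE.

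**The concern.** The number in 10.7 and the endpoint in 10.6.2 do not share a base. If the endpoint is a proportion of the subjects a reader scores suboptimal at UE-DSE, then 150 is the right number only if every evaluable subject is suboptimal at stress for every reader. Nothing in the plan ensures that. Entry is judged on an earlier resting examination, the efficacy set does not restrict on stress image quality, and the supportive analysis presupposes that some subjects are optimal at UE-DSE. Because the readers are analysed separately, the denominator can also differ between them.

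Two things are at stake. The stated precision is somewhat better than the endpoint can deliver. And since this co-primary is decided by a lower confidence limit, the choice of base can settle the result when the conversion rate is near its planned value.

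A smaller, related point is that 10.2 makes a border-delineation endpoint depend on a CAD diagnosis that the border score does not use.

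**Working it through.** **Inputs.** From 10.7: n = 150, expected proportion 0.45, two-sided 95% interval by normal approximation. From 10.6.4: threshold 35%. The share s of the 150 scored suboptimal at UE-DSE is not in the documents, so it is varied as an assumption.

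**Step 1: the plan's own figure.** Half-width = 1.96 × √(p(1 − p)/n) = 1.96 × √(0.45 × 0.55/150) = 7.96%. Lower limit = 45 − 7.96 = 37.0%. The stated 8% and the limit above 35% both reproduce. Since 175 × 0.85 = 148.75, the 150 is the evaluable number, with no further deduction.

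**Step 2: the same formula on the base in 10.6.2**, with n = 150 × s and 45% observed:

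| Assumed share s | n | Half-width | Lower limit |
|---|---|---|---|
| 100% | 150 | 8.0% | 37.0% |
| 90% | 135 | 8.4% | 36.6% |
| 80% | 120 | 8.9% | 36.1% |
| 70% | 105 | 9.5% | 35.5% |
| 60% | 90 | 10.3% | 34.7% |

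**Step 3: where the claim stops holding.** At 45% observed, a lower limit above 35% needs a half-width below 10 points, so n > 1.96² × 0.45 × 0.55/0.10² = 95.1. That means at least 96 subjects, or 96/150 = 64%. The half-width still rounds to 8% down to n = 132 (8.49%).

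**Step 4: the same data on two bases.** The smallest passing count is 65 of 150 (lower limit 35.4%) or 59 of 135 (35.3%). Over 150, 64 conversions give 34.75%, which fails. So with 135 of 150 suboptimal, any count from 59 to 64 passes over 135 and fails over 150. At a true conversion rate of 45% among the 135, the chance of a count in that window is about 39%. It falls to about 4% at 55% and 0.2% at 60%.

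**Step 5: the CAD truth requirement in 10.2.** If all 175 subjects were usable and suboptimal, the half-width would be 1.96 × √(0.2475/175) = 7.4%, against 8.0% at 150. That is a ceiling, not an expectation, because it ignores the planned dropout.

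**The case against.** The strongest reply is that the text already indicates the denominator. Section 10.6.2 speaks of suboptimal subjects who convert and sets a mirror-image analysis of optimal subjects beside it, which implies two complementary groups. On that reading the conclusion in 10.7 survives over a wide range. Subjects are selected for poor images at rest, and section 3 says stress makes imaging harder, so a share below 64% is not suggested anywhere. At a 90% share the lower limit falls by only 0.4 points. Additional enrolment for low CAD prevalence would enlarge the base. Most of this stands, and it limits the weight of the point. It does not supply a share: the up-to-30% figure in section 3 describes patients in general, not subjects selected for poor images at rest.

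Three stronger readings may tempt a reader, and the documents do not support them.

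- *That 10.7 contains an arithmetic error.* It does not; its figures reproduce at 150.
- *That the denominator is a free choice to be made once the data are in.* This goes too far, because 10.6.2 largely points to the conditional base. What is missing is a sentence that says so and a precision statement that follows it.
- *That the co-primary's chance of success is known to be badly off.* At a 90% share, one reader's chance of passing is 0.27 if 45% is a rate among suboptimal subjects but the endpoint counts all 150. It is 0.94 if 45% is a rate among all subjects but the endpoint is conditional. Both figures pair a rate on one base with an endpoint on the other, and the base of the prior rate is unknown. With both conditional it is 0.65, against 0.69 with both on all 150. The mismatched figures are illustrations only, and 10.7 claims no power for this endpoint.

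On 10.2, the reply is that few subjects will lack a diagnosis, since 10.6.1.1 classes a subject without angiography and without an event as negative. That is fair, and the gain from the change is small.

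**Conclusion.** The point holds as a mismatch between the endpoint's base and the sample-size base. The precision in 10.7 is computed on 150 subjects, while the endpoint as most naturally read has that many only if every evaluable subject is suboptimal at UE-DSE for the reader concerned. The size is modest at a high share: half-width 8.4% and lower limit 36.6% at 90%. The claim of a lower limit above 35% fails only below 96 subjects.

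These figures assume 150 evaluable subjects, 45% observed and shares that the documents do not give. The consequence for pass or fail is possible rather than certain: it disappears if nearly all subjects are suboptimal at stress, and is unlikely if conversion is well above 45%. The plan should be corrected, with medium confidence that it will matter in practice.

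**What to change.** 1. **10.6.2 and 10.6.4:** state that the denominator is the subjects with at least two adjacent inadequate segments in any apical view at UE-DSE, as scored by that reader, and tie the 35% rule to that proportion.
2. **10.7:** state the base of the prior 44.8%-46.0%, give an assumed share suboptimal at UE-DSE, and restate the half-width and lower limit on the resulting number. No further enrolment is needed for this.
3. **10.2:** analyse the border-delineation endpoints in all dosed subjects with peak-stress data from both UE-DSE and CE-DSE, whether or not a CAD truth diagnosis is available. Keep the present set for sensitivity and specificity.

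The cost is wording in four sections, a slightly less favourable stated precision and one extra analysis set.

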10.8 Data Handling

All data collected will be entered into the database and displayed in the data listings and/or tables. Details of the data handling procedures will be specified in the SAP.

10.9 Interim Analyses

No interim analysis is planned.

11 Ethics and Good Clinical Practice

11.1 Ethical and Regulatory Compliance

The study will be conducted in accordance with the protocol, ICH, Good Clinical Practice, FDA regulations, ethical principles that have their origin on the Declaration of Helsinki and all applicable local regulations, whichever offers greatest protection for the subject.

11.2 Informed Consent and Subject Information

All subjects must sign and personally date an approved Informed Consent Form after receiving detailed written and verbal information about the reason, the nature and the possible risks associated with the administration of the IP/IMP and NIMP(s). This must be done according to the guidelines provided in the Declaration of Helsinki, ICH E6 Guideline for Good Clinical Practice, and as applicable, the requirements of Title 21 CFR 50.20 through 50.27 and the EU Directive 2001/20/EC, 2005/28/EC, and related guidance, and applicable laws and regulations of Health Canada.

The subject must be made aware and agree that personal information may be scrutinized during inspection or audit by competent authorities and properly authorized persons. However, personal information will be treated as strictly confidential and will not be publicly available in accordance to the Guidelines for Data Processing within the Framework of Clinical Drug Trials 24 July 2008.

11.3 Institutional Review Board/Ethics Committee/Research Ethics Board Approval

The protocol, Informed Consent Form, Subject Information Sheet, if applicable, and any advertisement for the recruitment of subjects must be reviewed and approved by an appropriately constituted IRB/EC/REB, as required in chapter 3 of the ICH E6 Guideline, and as applicable, Title 21 CFR 56.107 through 56.115 and EU Directive 2001/20/EC, 2005/28/EC, and related guidance, and applicable laws and regulations of Health Canada. Written IRB/EC/REB approval must be obtained by Sponsor prior to shipment of IP/IMP or subject enrollment.

The Investigator is committed in accordance with local requirements to inform the IRB/EC/REB of any emergent problem, serious adverse events, and/or protocol amendments.

11.4 Financial Disclosure

Financial support to Investigators/Sub-investigators other than the cost of conducting the clinical study or other clinical studies will be disclosed where applicable in accordance with Title 21 CFR 54.2 to 54.6 and the EU Directive 2001/20/EC, 2005/28/EC and related guidance.

11.5 Safety Monitoring Boards

There will be no safety monitoring board for this study.

12 Administrative Considerations

12.1 Regulatory Requirements—Sponsor/Investigator Obligations

This study will be conducted in accordance with the Declaration of Helsinki, ICH E6 Guideline, and as applicable, Title 21 CFR 312.50 through 312.70, and EU Directive 2001/20/EC and 2005/28/EC related guidance, and applicable laws and regulations of Health Canada. To ensure compliance the Investigator agrees, by written consent to this protocol, to fully cooperate with compliance checks by allowing access to all documentation by authorized individuals, and competent and regulatory authorities.

12.2 Sponsor Regulatory Obligations for SUSARs Reporting

The Sponsor shall ensure that all relevant information about suspected unexpected serious adverse reaction (SUSAR) which occurs during the course of the clinical trial, whether or not this event is fatal or life-threatening, will be reported to the applicable Regulatory Authority/Competent Authorities including but not limited to FDA, Health Canada or any European Economic Area State in which the trial is being conducted and to the relevant ECs in accordance with EU Directive 2011/C 172/01 about Communication from the Commission — Detailed guidance on the collection, verification and presentation of adverse event/reaction reports arising from clinical trials on medicinal products for human use ('CT-3').

12.3 Protocol Amendment

No change to the protocol may be made without the joint agreement of both the Investigator and Sponsor. Any amendment to the original protocol will be signed by both parties and submitted to the IRB/EC/Competent Authority (CA)/REB for approval or notification prior to implementation except in circumstances when it is necessary to implement urgent safety measures to remove an immediate hazard to the study subject(s).

12.4 Curriculum Vitae

The Investigator and any sub-investigator(s) must provide Sponsor with current copies of their own signed and dated curriculum vitae.

12.5 Administrative Structure

The administrative structure of the study (e.g., monitoring and vendor personnel, statistician, laboratory facilities, and clinical trial supply management) is presented in Appendix F. A complete and controlled list of the Investigators, study sites, and IRBs/ECs/REBs involved in this study can be found in the Trial Master File maintained by the Sponsor.

12.6 Protocol Deviations, Violations and Exceptions

As a matter of policy, Bracco will not grant exceptions to protocol-specific entry criteria to allow subjects to enter a study. If investigative center personnel learn that a subject who did not meet protocol eligibility criteria was entered in a study they must immediately inform Bracco.

If a violation is serious, and meet the definition of a serious breach the Clinical Research Manager (CRM) takes appropriate action according to the requirements and timelines stated the Code of Federal Regulations (CFR), European Guidance and local regulations as applicable.

12.7 Monitoring Procedures

12.7.1 Study Monitoring

An appropriate representative of Sponsor (Study Monitor) will maintain contact with the Investigator and will visit the study site for the purpose of discussing and/or retrieving data.

An initiation visit will be made by the Study Monitor to discuss the protocol and the obligations of both the Sponsor and the Investigator. The Investigator must allow the Study Monitor to perform periodic, interim monitoring visits. The purposes of these visits are to:

- verify that written Informed Consent was obtained prior to each subject's participation in the study;
- assess the progress of the study;
- review the compliance with the study protocol;
- determine whether all adverse events were appropriately reported;
- determine whether the Investigator is maintaining the essential documents;
- discuss any emergent problem;
- check the Case Report Forms for legibility, accuracy and completeness;
- validate the contents of the Case Report Forms against source documents;
- assess the status of IP/IMP storage, dispensing and retrieval.

All data required by the protocol must be reported accurately on the Case Report Form and must be consistent with the source documents. Source documents are original documents, data and records (e.g., hospital records, clinical and office charts, laboratory notes, memoranda, subjects' diaries or evaluation checklists, pharmacy dispensing records, recorded data from automated instruments, copies, magnetic media, X-rays or other diagnostic images, subject files, laboratory records). The Investigator will make available the source documents for inspection. This information will be considered confidential.

The Study Monitor will perform a close-out visit at the conclusion of the Investigator's involvement in the study.

